9.1.3 Per Protocol (PP) set

The Per Protocol (PP) set will include all patients in the FAS without major protocol deviations, as will be defined in the Patient Validation Document. Results of the primary efficacy endpoints conducted in the PP set will be considered as supportive.

In addition to the primary analysis, the primary efficacy variable will also be analyzed using the same primary analysis model on the PP set as supportive information.

9.1.4 Safety population

The safety population will include all patients who received any amount of study treatment or standard of care treatment and who have at least one post-baseline safety assessment. Of note, the statement that a patient had no adverse events also constitutes a safety assessment. Patients will be analyzed according to treatment received. The analyses on safety parameters will be conducted in the Safety set.

9.2 Patient demographics and other baseline characteristics

All data about patient demographics and baseline characteristics, including derived variables, will be summarized in the FAS, overall and by treatment group, by means of summary descriptive statistics. Continuous data will be summarized by the mean, standard deviation (SD), median, first and third quartiles, minimum and maximum. Categorical data will be presented by absolute and relative frequencies (n and %) or contingency tables.

In order to interpret the results adequately, the homogeneity of patients' distribution between treatment groups will be tested on demographics and anamnestic variables. P-values will have a descriptive meaning and any warnings of heterogeneity will be evaluated considering the clinical relevance of the involved variables. The p-values will not be considered to define any formal basis for determining factors to be included in statistical models. If an imbalance of treatment groups with respect to some variables does occur, supplemental analyses with addition of these variables in model may be performed to assess the potential impact on efficacy as appropriate. For continuous variables, the homogeneity of data will be tested by means of t-test. If data do not respect normality assumption a Wilcoxon rank sum test will be applied. For categorical variables chi-square test will be used. Fisher exact test in case of cell frequencies less than 5 will be applied.

Whenever necessary, normality will be assessed by means of Shapiro-Wilk test and with graphical methods. In case of non-normality, appropriate transformation of data will be applied or a non-parametric test/model will be adopted.

The number and percentages of subjects meeting all eligibility criteria at screening will be provided. The number of the analysis populations will be described and the reasons excluding the patient from any particular population will be provided with the number of protocol violators per each criterion.

A complete description of patient disposition will be provided, overall and by treatment group specifying the number of randomized patients, number of patients at each visit, completed and discontinued patients, and the reason for the discontinuation.

The difference between treatment groups with respect to protocol violations and reasons for drop-out will be examined.

Medical history data will be presented by System Organ Class and Preferred Term, overall and by treatment group.

9.3 Treatments

9.3.1 Investigational Treatment

Overall study treatment administration details will be summarized for the FAS and the Safety population in the serelaxin arm only. This will include time from presentation to randomization (in hours), time from randomization to study treatment initiation (in hours), time from presentation to study treatment initiation (in hours), study treatment administered (yes/no), reason study treatment not administered, actual treatment received, and the number of days study treatment infused (one or two). The duration of study treatment administration (in hours) and the total volume of study treatment administered (estimated from the total time and rate of infusion) will be summarized. In addition, the number of subjects whose study medication dose was lowered or discontinued prematurely, and the reasons for discontinuation, will be summarized. Logistic regression models will be fitted considering demographics and anamnestic factors in order to identify main predictors for drug discontinuation. Odds ratio and 95% confidence intervals will be provided.

9.3.2 Concomitant treatments

Concomitant treatment administration details will be collected at any time between start of screening and randomization as well as by day from randomization. It will be summarized for the FAS and the Safety population. In addition, concomitant treatment administration details collected overall during index hospitalization and after discharge will also be summarized for the FAS and the Safety population.

As a patient may have taken more than one medication, the total number of medications could be greater than the total number of subjects. Continuous variables will be summarized with standard summary statistics (number of observations, mean, standard deviation, median, first and third quartiles, minimum and maximum), categorical variables with the number and percentage of subjects taking at least one dose of medication. Percentages will be computed on patients included in the analysis population.

The total dose of IV loop diuretic and oral loop diuretic administered during the index hospitalization will be compared between treatment groups using a t-test. Doses will be converted to furosemide equivalents for analysis.

Any standard of care treatment given according to local guidelines/international standards will be summarized by preferred term.

This treatment can include but is not limited to intravenous and/or oral diuretics, ACE inhibitors/angiotensin receptor antagonists, β blockers, and aldosterone receptor antagonists, etc. Summary tables will also be provided by country.

As to the rescue medication usage summary statistics will be provided by treatment group. The rescue medication can include the institution or up-titration of IV furosemide, IV nitrates or any other IV medication for heart failure, or institution of mechanical support such as assisted (invasive or non-invasive) ventilation, ultrafiltration, hemodialysis, intra-aortic balloon pump or ventricular assist device, etc.

The use of other non-cardiovascular concomitant medications and significant non-drug therapies, prior to and after the randomization date, respectively, will be summarized by treatment group, therapeutic class, and preferred term for the FAS and the Safety population.

9.4 Analysis of the primary variable(s)

The primary analysis and the analyses of all secondary and exploratory efficacy variables will be based on the FAS.

9.4.1 Variable(s)

The primary efficacy variable of the study is the time to in-hospital Worsening of Heart Failure (WHF) requiring rescue therapy or all-cause death through Day 5 post randomization.

In-hospital worsening of heart failure (WHF) through Day 5 post randomization, includes worsening signs and/or symptoms of heart failure that require an intensification of intravenous therapy for heart failure or mechanical ventilation, renal or circulatory support. Such treatment can include the institution or up-titration of IV furosemide, IV nitrates or any other IV medication for heart failure, or institution of mechanical support such as assisted (invasive or non-invasive) ventilation, ultrafiltration, hemodialysis, intra-aortic balloon pump or ventricular assist device, etc. This endpoint also includes patients who die in this 5-day period of any cause before experiencing episode(s) of WHF.

A central event adjudication committee will be appointed and will oversee the WHF primary endpoint adjudication.

9.4.2 Statistical model, hypothesis and method of analysis

Time to in-hospital WHF/all-cause death through Day 5 post randomization will be analyzed using survival analysis.

The time to in-hospital WHF/all-cause death will be computed as the number of hours from randomization to the earlier of the onset of in-hospital WHF or death. The onset of in-hospital worsening heart failure through Day 5 will be the first assessment point, in terms of date and time, at which the investigator reported worsening heart failure (either during the initial hospitalization or re-hospitalization for heart failure). Subjects without an event will be censored at the earlier of the last assessment or 120 hours after randomization.

The primary statistical hypothesis is:

$H_0: \lambda_2/\lambda_1 \geq 1$, i.e., the rate of primary event of in-hospital WHF or all cause death is greater or equal in the serelaxin group relative to the standard of care group versus the one-sided

alternative H_A : $\lambda_2/\lambda_1 < 1$, i.e., the rate of in-hospital WHF or all cause death is smaller in the serelaxin group relative to the standard of care group, where λ_1 and λ_2 are the hazard rates for in-hospital WHF or all cause death in the standard of care group and serelaxin group, respectively. The ratio λ_2/λ_1 is also called the hazard ratio of serelaxin to standard of care.

The hypothesis will be tested based on the FAS with a Gehan's generalized Wilcoxon test at a significance level of 0.025 (one-sided). Patients without an event will be censored at the earlier of the last contact date or 120 hours after randomization.

The Kaplan-Meier estimates of the survival functions for each treatment group will be plotted and Kaplan-Meier estimates for selected time points with 95% confidence intervals will be tabulated.

The hazard ratio (relative risk) and its associated two-sided 95% confidence interval will be estimated based on a Cox proportional hazards model with treatment assignment as a factor. Absolute frequencies and proportions of patients with in-hospital WHF or all-cause death through Day 5 in each treatment group will be also provided.

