9.4.3 Handling of missing values/censoring/discontinuations

In the analysis on time to in-hospital WHF/all-cause death through Day 5, patients without any event will be censored at the earlier of the last assessment or 120 hours post randomization.

The proportions of patients with in-hospital WHF/all-cause death through Day 5 in each treatment group will be presented on all patients included in the efficacy analysis set.

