5.2. EFFICACY DATA

The primary analysis and the analyses of all secondary and exploratory efficacy variables will be based on the FAS. In addition to the primary analysis, the primary efficacy variable will also be analysed using the same primary analysis model on the PP set as supportive information.

Primary efficacy parameter

Worsening Heart Failure/all cause death through Day 5

The primary efficacy variable of the study is the time to in-hospital Worsening of Heart Failure (WHF) requiring rescue therapy or all cause death through Day 5 post randomization.

In-hospital worsening of heart failure (WHF) through Day 5 post randomization includes worsening signs and/or symptoms of heart failure that require an intensification of intravenous therapy for heart failure or mechanical ventilation, renal or circulatory support. Such treatment can include the institution or up-titration of IV furosemide, IV nitrates or any other IV medication for heart failure, or institution of mechanical support such as assisted (invasive or non-invasive) ventilation, ultrafiltration, hemodialysis, intra-aortic balloon pump or ventricular assist device, etc. This endpoint also includes patients who die in this 5-day period of any cause before experiencing episode(s) of WHF.

Time to in-hospital WHF/all cause death through Day 5 post randomization will be analysed using survival analysis.

The time to in-hospital WHF/all cause death will be computed as the number of hours from randomization to the earlier of the onset of in-hospital WHF or death plus 1 minute. The onset of in-hospital worsening heart failure through Day 5 will be the start date/time of event

Statistical Analysis Plan

Sponsor: NOVARTIS

Protocol number: CRLX030A3301

reported at the first assessment point at which the investigator reported worsening heart failure; if death occurred, date and time are reported in the dedicated eCRF section. Subjects without an event will be censored at the earlier of the last post-baseline assessment date or 120 hours after randomization. Subjects without any information after baseline (i.e., randomization) will be considered censored at 1 minute.

In case of missing time of in-hospital WHF or death then 00:00 will be imputed.

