Only adjudicated endpoints will be counted in the primary analysis. The “adjudicated endpoint” refers to an endpoint and date of the endpoint that has been confirmed by an independent adjudication committee who has no access to the treatment code. According to the information from the endpoint adjudication committee, the following rules will be applied to determine if an event reported in eCRF should be considered valid for the analysis or not:

Table 5.2-1: Rule for inclusion of events into the analysis

Included in the analysis	
WHF/death reported in the dedicated page of the eCRF and confirmed by adjudication committee	YES
WHF/death reported in the dedicated page of the eCRF and NOT confirmed by adjudication committee	NO

If more than one in-hospital WHF occurred, the first one will be used as the event. Censoring and time will be defined according to the following rule:

Table 5.2-2: Censoring and time rules

	Status	Time
At least one in hospital WHF and/or death occurred and:		
Difference between date and time of first occurrence of WHF/death and date and time of randomization +1 minute >120 hours	Censored	120h
Difference between date and time of first occurrence of WHF/death and date and time of randomization +1 minute \leq 120 hours	Event	Calculated difference
No in hospital WHF and death occurred and:		
Difference between date and time of last assessment* and date and time of randomization +1 minute >120 hours	Censored	120h
Difference between date and time of last assessment* and date and time of randomization +1 minute \leq 120 hours	Censored	Calculated difference

* Last assessment is the date and time of last available post-baseline physician assessment of in-hospital WHF

In case a patient is lost to follow-up, events occurring prior to the time of lost to follow-up will be counted. If no event occurred, then the patient will be censored at the time of last post-baseline in-hospital WHF assessment available.

The primary statistical hypothesis is:

	Statistical Analysis Plan
	Sponsor: NOVARTIS Protocol number: CRLX030A3301

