An additional supportive analysis of the primary efficacy variable will be performed using all WHF/all cause deaths through Day 5 post randomisation as reported by the investigators, regardless of confirmation from the endpoint adjudication committee.

The time to WHF/all cause deaths through Day 5 post randomisation will be as described for the primary analysis.

	Statistical Analysis Plan
	Sponsor: NOVARTIS
	Protocol number: CRLX030A3301

The Kaplan-Meier estimates of the survival functions for each treatment group will be plotted. Kaplan-Meier estimates at selected time points and their 95% confidence intervals will be provided.

Handling of missing values/censoring/discontinuations

In the analysis of time to in-hospital WHF/all-cause death through Day 5, patients without any event will be censored at the earlier of the last post-baseline physician assessment of in-hospital WHF or 120 hours post randomization.

Subjects without any information after baseline (i.e., randomization) will be considered censored at 1 minute.

In case of missing time of in-hospital WHF or death then 00:00 will be imputed.

Secondary efficacy parameters

The additional efficacy endpoints will be analysed in the FAS. Standard descriptive statistics will be presented for each treatment group at each time point that the endpoint was measured. Two-sided p-values <0.05 will be considered statistically significant; no adjustment for multiple comparisons will be adopted.

Time to in-hospital WHF/All cause death/readmission for heart failure through Day 14 post randomization

Time to in-hospital WHF/all cause death/readmission for heart failure through Day 14 post randomization will be analyzed using survival analysis.

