Difference between date and time of first occurrence of WHF/death/readmission for HF and date and time of randomization +1 minute ≤336 hours	Event	Calculated difference
No in hospital WHF/death/readmission for HF occurred and: Difference between date and time of last assessment* and date and time of randomization +1 minute >336 hours	Censored	336h
Difference between date and time of last assessment* and date and time of randomization +1 minute ≤336 hours	Censored	Calculated difference

* Last assessment is the date and time of last available post-baseline physician assessment of in-hospital WHF

In case a patient is lost to follow-up, only the data until the last post-baseline in-hospital WHF assessment available will be considered in the analysis.

Treatment groups will be compared with a Gehan's generalized Wilcoxon test. The Kaplan-Meier estimates of the survival functions for each treatment group will be plotted. The Kaplan-

	Statistical Analysis Plan
	Sponsor: NOVARTIS Protocol number: CRLX030A3301

Meier estimates of the cumulative event rate will also be presented in tables by treatment group for each day and also by time interval (>0-5 days, >5-14 days).

Absolute frequencies and proportions of patients with event (as defined in the time to event analysis), overall (in-hospital WHF/all cause death/readmission) and by type of event (in-hospital WHF; all cause death; readmission), through Day 14 in each treatment group will also be provided (percentages based on population of analysis).

In addition, a description of all in-hospital WHF that occurred through Day 14 will be provided: absolute frequencies and proportions of patients with in-hospital WHF at each assessment time point will be presented overall and by the concomitant medication given (new, restarted or increased dose of medication), and/or by the need of mechanical/surgical intervention (yes/no) for the in-hospital WHF.

A summary of number and percentage of patients with or without WHF events through Day 5 (recorded on “Clinical worsening of heart failure” eCRF page for adjudicated events), and from Day 6 through Day 14 (recorded on “Heart failure details” eCRF page for events not to be adjudicated), will be provided by treatment.

Persistent signs or symptoms of HF/ non-improvement

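### Protocol 9.4.2 gives two censoring times for the primary endpoint, and the SAP rule ends event-free follow-up sooner than it stops counting events

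*Protocol*

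**What the plan says.** **Protocol.** Section 9.4.2 first states: "Subjects without an event will be censored at the earlier of the last assessment or 120 hours after randomization". After naming the Gehan test it states: "Patients without an event will be censored at the earlier of the last contact date or 120 hours after randomization". Section 9.4.3 and the synopsis agree with the first version: "patients without any event will be censored at the earlier of the last assessment or 120 hours post randomization".

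**SAP, Day 5 endpoint.** The text of 5.2 reads: "Subjects without an event will be censored at the earlier of the last post-baseline assessment date or 120 hours after randomization". The footnote to Table 5.2-2 narrows this: "Last assessment is the date and time of last available post-baseline physician assessment of in-hospital WHF". The paragraph on missing values repeats the narrower form: "patients without any event will be censored at the earlier of the last post-baseline physician assessment of in-hospital WHF or 120 hours post randomization". For events, Table 5.2-2 uses only one elapsed time, the "Difference between date and time of first occurrence of WHF/death and date and time of randomization +1 minute". If that is 120 h or less the patient has an event, whenever the last WHF assessment took place. Only adjudicated events count.

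**SAP, Day 14 endpoint.** For patients lost to follow-up, "only the data until the last post-baseline in-hospital WHF assessment available will be considered in the analysis". The matching sentence for the Day 5 endpoint instead counts events up to the time of loss.

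SAP 5.1 says the data are analysed as set out in Section 9 of the protocol, so both protocol rules are carried in by reference.

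**The concern.** Last contact and last assessment are different times in this trial. The protocol plans contacts with no WHF assessment, such as telephone calls about survival for patients who do not return (Section 6) and a call if Day 14 cannot be attended (3.1). Two analysts working from 9.4.2 could build different primary datasets.

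The SAP's choice also treats outcomes unequally. After the last WHF assessment a death still enters the analysis, while survival without readmission does not. Censoring should not depend on how the patient fared. Treatment is open label and may change length of stay, so attendance after discharge could differ between arms. A difference of that kind could reach the treatment comparison.

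**Working it through.** **1. Who is affected.** WHF is also assessed at Day 14 (Protocol 6.4.1, Table 6-1). Take a patient discharged on Day 3 who misses Day 5, and apply Table 5.2-2:

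- Attends Day 14, no event: the last WHF assessment is after 120 h, so censored at 120 h.
- Reached only by phone at Day 14, alive and not readmitted: censored at the Day 3 assessment.
- Died on Day 4, adjudicated: event on Day 4.

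Only the second kind of patient, with no WHF assessment at or after 120 h, is cut short.

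**2. Inputs.** From the documents: a 120 h horizon; 2:1 allocation of 3183 patients, hence 2122 and 1061; Day 5 rates of 6.5% and 12.0% in the earlier phase III trial (Protocol 1.1), used only for scale. Those rates reproduce the quoted odds ratio: (6.5/93.5)/(12.0/88.0) = 0.51. The inputs to the sample size are redacted and are not needed here. Assumed, because the documents are silent: a share q of affected patients; last assessment L uniform on 48–120 h or 96–120 h; constant hazard; deaths 10% to 40% of events; no in-hospital WHF after L.

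**3. Shift in the Kaplan-Meier rate.** Compare the SAP rule with following known event-free patients to 120 h. At time t the SAP risk set is short by about q·F(t), where F(t) is the probability that L has passed. The cumulative hazard is too high by about λ·q·a, where λ = −ln(1−p)/120 and a is the integral of F to 120 h: 72/2 = 36 h, or 24/2 = 12 h. The rate shifts by about (1−p)·λ·q·a.

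- p = 12.0%: λ = 0.1278/120 = 0.001065. With q = 10%, a = 36: 0.88 × 0.001065 × 0.10 × 36 = 0.0034, or 0.34 points. With a = 12: 0.11 points.
- p = 6.5%: λ = 0.0672/120 = 0.000560. With q = 10%: 0.19 and 0.06 points.
- q = 5% halves each: 0.17, 0.06, 0.09 and 0.03 points.

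Simulation with 3 million patients agrees:

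| q | shift at 12.0% | shift at 6.5% |
|---|---|---|
| 2% | 0.02–0.07 | 0.01–0.04 |
| 5% | 0.06–0.17 | 0.03–0.10 |
| 10% | 0.11–0.35 | 0.06–0.19 |
| 20% | 0.23–0.72 | 0.13–0.40 |

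The part due only to counting deaths after L is at most 0.14 points at q = 10%.

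**4. Extreme bound.** If 10% of event-free patients were censored immediately, the rate becomes p/(p + 0.9(1−p)): 0.12/0.912 = 13.2% and 0.065/0.9065 = 7.2%.

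**5. Hazard ratio and test.** Both arms had an assumed rate of 8%, with 4000 runs (standard error √(0.025 × 0.975/4000) = 0.0025). With q = 10% in each arm, the one-sided Gehan test rejects in 0.0248 of runs under the SAP rule and 0.0245 under the known-status rule; the mean hazard ratio is 1.007 under both. With 6.5% versus 12.0%, the ratio is 0.528 under both. With unequal shares at 8%:

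| q serelaxin / SOC | HR known-status | HR SAP | SAP ÷ known | reject known-status | reject SAP |
|---|---|---|---|---|---|
| 10% / 5% | 0.992 | 1.007 | 1.015 | 0.0260 | 0.0200 |
| 5% / 10% | 1.015 | 1.000 | 0.985 | 0.0222 | 0.0278 |
| 20% / 10% | 0.976 | 1.007 | 1.032 | 0.0415 | 0.0255 |
| 10% / 20% | 1.028 | 0.996 | 0.969 | 0.0192 | 0.0312 |
| 30% / 10% | 0.955 | 1.018 | 1.066 | 0.0535 | 0.0203 |

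The rules differ on the hazard ratio by about 36/120 = 0.3 times the difference in q, so roughly 3% per 10 points. In these runs no WHF follows L, so the arm with more early last assessments truly has fewer endpoint events. Known-status rejections above 0.025 reflect that built-in difference. They would be false rejections if WHF did occur after L and went unrecorded, which bears on the fix.

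**The case against.** **The SAP is operationally clear.** Its tables yield one rule, and the synopsis, 9.4.3 and the first statement in 9.4.2 all use last assessment. A reader might infer three competing rules. The documents do not support that: the SAP wording defines the protocol's last assessment. What remains is one conflicting sentence, placed beside the primary test in the section to which the SAP defers.

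**Few patients are exposed.** Inpatients are assessed daily, early discharges must return at Days 5 and 14, and the Amendment 2 rationale expects most discharges after Day 5. This stands. A reader might think that missing Day 5 is enough to be censored at discharge; attendance at Day 14 prevents it.

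**The direction is conservative.** The mechanism the documents suggest is shorter stay on serelaxin. That would put more early censoring in the serelaxin arm, raise its estimated rate and work against rejection. This also stands.

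**WHF status is unknown after the last assessment.** In part. The endpoint is in-hospital WHF, so a discharged patient known not to be readmitted cannot have had it. A call that establishes survival alone does not show this.

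**The per-protocol analysis covers it.** Missing the Day 5 visit is listed as a major deviation in SAP Table 3-1. Removing such patients selects on attendance; it does not restore their follow-up.

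**The Day 14 sentence runs the other way.** Correct. For patients lost to follow-up it would drop deaths after the last WHF assessment. It is an inconsistency between endpoints and no evidence for the Day 5 asymmetry.

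**Conclusion.** The conflict within Protocol 9.4.2 and the outcome-dependent censoring in SAP Table 5.2-2 are both real and should be corrected. The expected numerical effect is small. At 5% to 10% affected, Kaplan-Meier rates rise by about 0.03 to 0.35 points, while the hazard ratio and type I error are almost unchanged if the arms are affected alike. These sizes rest on assumed shares, assessment times and death fractions, since the documents give none.

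A reader might conclude that the plan materially inflates event rates or the false-positive risk. The calculations do not show that. The upward push applies to Kaplan-Meier and hazard estimates only, and crude proportions use all patients. Under the SAP rule with unequal shares, rejection ranged from 0.020 to 0.031. The residual exposure is differential missingness, conservative if shorter stay on serelaxin is its cause. The firmer reason to act is that a primary analysis should have one censoring rule that does not depend on outcome.

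**What to change.** Use one rule in both documents:

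- Censor event-free patients at the earlier of 120 h (336 h for Day 14) or the last time they are known to be alive and without in-hospital WHF or heart-failure readmission. Any visit, discharge record, readmission record or phone contact may supply this. A contact that records survival only does not qualify by itself.
- Keep counting every adjudicated WHF and death within 120 h. The common rule must not be read as removing deaths in the first five days, which belong to the endpoint.
- Replace the Day 14 loss-to-follow-up sentence with one that matches the Day 5 rule.
- Delete the conflicting sentence in Protocol 9.4.2, or state in the SAP which rule governs.
- Keep censoring at the last WHF assessment as a sensitivity analysis, and report by arm how many patients had no such assessment at or after 120 h.

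The cost is wording and one extra run. Vital status and repeat hospitalization are already collected to Day 30, and the SAP already censors Day 30 mortality at the last date known alive.
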